6.3.4 Endocrine Disorders or Events

Immune-related endocrine events are a potential risk with tiragolumab.

Management guidelines for endocrine events are provided in the table below.

Patients with unexplained symptoms such as headache, fatigue, myalgias, impotence, constipation, or mental status changes should be investigated for the presence of thyroid, pituitary, or adrenal endocrinopathies. The patient should be referred to an endocrinologist if an endocrinopathy is suspected. Thyroid-stimulating hormone (TSH) and free triiodothyronine and thyroxine levels should be measured to determine whether thyroid abnormalities are present. Pituitary hormone levels and function tests (e.g., TSH, growth hormone, luteinizing hormone, follicle-stimulating hormone, testosterone, prolactin, adrenocorticotrophic hormone [ACTH] levels, and ACTH stimulation test) and magnetic resonance imaging (MRI) of the brain (with detailed pituitary sections) may help to differentiate primary pituitary insufficiency from primary adrenal insufficiency.

Management Guidelines for Endocrine Disorders or Events

| Event | Management |
|------------------------------|---|
| Hypothyroidism, Grade 1 | 
 ● Continue atezolizumab and tiragolumab. ● Initiate treatment with thyroid replacement hormone. ● Monitor TSH closely. |
| Hypothyroidism, Grade 2 | 
 ● Consider withholding atezolizumab and tiragolumab. ● Initiate treatment with thyroid replacement hormone. ● Monitor TSH closely. ● Consider patient referral to endocrinologist. ● Resume atezolizumab and tiragolumab when symptoms are controlled and thyroid function is improving. |
| Hypothyroidism Grade 3 and 4 | 
 ● Withhold atezolizumab and tiragolumab ● Initiate treatment with thyroid replacement hormone. ● Monitor TSH closely ● Refer to an endocrinologist ● Admit patient to the hospital for developing myxedema (bradycardia, hypothermia, and altered mental status) ● Resume atezolizumab when symptoms are controlled, and thyroid |

| Event | Management |
|---|--|
| | 
function is improving.
 
 ● Permanently discontinue atezolizumab.^c |
| Hyperthyroidism, Grade 1 | 
TSH \geq 0.1 mU/L and $<$ 0.5 mU/L:
 
 ● Continue atezolizumab and tiragolumab. ● Monitor TSH every 4 weeks. ● Consider patient referral to endocrinologist 
TSH $<$ 0.1 mU/L:
 
 ● Follow guidelines for Grade 2 hyperthyroidism. ● Consider patient referral to endocrinologist |
| Hyperthyroidism, Grade 2 | 
 ● Consider atezolizumab and tiragolumab. ● Initiate treatment with anti-thyroid drug such as methimazole or carbimazole as needed. ● Consider patient referral to endocrinologist. ● Resume atezolizumab and tiragolumab when symptoms are controlled and thyroid function is improving. |
| Grade 3 and 4 hyperthyroidism | 
 ● Withhold atezolizumab. ● Initiate treatment with anti-thyroid drug such as methimazole or carbimazole as needed. ● Refer to an endocrinologist. ● Resume atezolizumab and tiragolumab when symptoms are controlled, and thyroid function is improving. ● Permanently discontinue atezolizumab.^c |
| Adrenal insufficiency, Grade 2–4 | 
 ● Withhold atezolizumab and tiragolumab for up to 12 weeks after event onset.^a ● Refer patient to endocrinologist. ● Perform appropriate imaging. ● Initiate treatment with corticosteroids equivalent to 1–2 mg/kg/day IV methylprednisolone and convert to 1–2 mg/kg/day oral prednisone or equivalent upon improvement. ● If event resolves to Grade 1 or better and patient is stable on replacement therapy, resume atezolizumab and tiragolumab.^b ● If event does not resolve to Grade 1 or better or patient is not stable on replacement therapy while withholding atezolizumab and tiragolumab, permanently discontinue atezolizumab and tiragolumab and contact PI.^c |
| Hypophysitis (panhypopituitarism), Grade 2 or 3 | 
 ● Withhold atezolizumab and tiragolumab for up to 12 weeks after event onset.^a ● Refer patient to endocrinologist. ● Perform brain MRI (pituitary protocol). ● Initiate treatment with corticosteroids equivalent to 1–2 mg/kg/day IV methylprednisolone and convert to 1–2 mg/kg/day oral prednisone or equivalent upon improvement. ● Initiate hormone replacement if clinically indicated. ● If event resolves to Grade 1 or better, resume atezolizumab and tiragolumab.^b |

| Event | Management |
|--|---|
| | 
 ● If event does not resolve to Grade 1 or better while withholding atezolizumab and tiragolumab, permanently discontinue atezolizumab and tiragolumab and contact PI. ^c ● For recurrent hypophysitis, treat as a Grade 4 event. |
| Hypophysitis (panhypopituitarism), Grade 4 | 
 ● Permanently discontinue atezolizumab and tiragolumab and contact Medical Monitor. ^c ● Refer patient to endocrinologist. ● Perform brain MRI (pituitary protocol). ● Initiate treatment with corticosteroids equivalent to 1–2 mg/kg/day IV methylprednisolone and convert to 1–2 mg/kg/day oral prednisone or equivalent upon improvement. ● Initiate hormone replacement if clinically indicated. |

MRI = magnetic resonance imaging; TSH = thyroid-stimulating hormone.

^a Atezolizumab and tiragolumab may be withheld for a longer period of time (i.e., > 12 weeks after event onset) to allow for corticosteroids (if initiated) to be reduced to the equivalent of ≤ 10 mg/day oral prednisone. The acceptable length of the extended period of time must be based on the investigator's benefit-risk assessment and in alignment with the protocol requirements for the duration of treatment and documented by the investigator.

^b If corticosteroids have been initiated, they must be tapered over ≥ 1 month to the equivalent of ≤ 10 mg/day oral prednisone before atezolizumab and tiragolumab can be resumed.

^c Resumption of atezolizumab and tiragolumab may be considered in patients who are deriving benefit and have fully recovered from the immune-mediated event. The decision to re-challenge patients with atezolizumab should be based on the investigator's benefit-risk assessment and documented by the investigator.

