6.0 DOSE DELAYS/DOSE MODIFICATIONS

Other holds and modifications beyond what is described below may be made at the discretion of the PI.

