6.2.1 Study treatment discontinuation criteria specific to tiragolumab or atezolizumab-related AEs

- Any Grade ≥ 2 treatment-related uveitis, eye pain, or blurred vision that does not respond to topical therapy and does not improve to Grade 1 severity within 8 weeks or requires systemic treatment.

- Any Grade ≥ 2 treatment-related pneumonitis or interstitial lung disease that does not resolve following dose delay and systemic steroids.
- For Grade ≥ 3 adrenal insufficiency or Grade ≥ 4 hypophysitis, treatment needs to be discontinued regardless of control with hormone replacement (Note: Hospitalization for diagnostic workup of adrenal insufficiency without severe symptoms should not require discontinuation).
- Any Grade ≥ 3 non-skin, treatment-related AE lasting > 7 days or recurs, with the following exceptions for uveitis, pneumonitis, bronchospasm, diarrhea, colitis, neurologic toxicity, hypersensitivity reactions, infusion reactions, endocrinopathies, and laboratory abnormalities:
 - Grade 3 treatment-related uveitis, pneumonitis, bronchospasm, diarrhea, colitis, neurologic toxicity, hypersensitivity reaction, or infusion reaction of any duration requires discontinuation.
 - Grade 3 treatment-related endocrinopathies (excluding adrenal insufficiency and hypophysitis) adequately controlled with only physiologic hormone replacement do not require discontinuation.
 - Grade 3 treatment-related laboratory abnormalities do not require treatment discontinuation except:
 - Grade 3 treatment-related thrombocytopenia > 7 days or associated with clinically significant bleeding requires discontinuation.
- In most cases of Grade 3 AST or ALT elevation, study treatment will be permanently discontinued. If the Investigator determines a possible favorable benefit/risk ratio that warrants continuation of study treatment, a discussion between the Investigator and the Medical Monitor/designee must occur.
- Any treatment-related liver function test abnormality that meets the following criteria require discontinuation:
 - AST or ALT $> 5 \times$ ULN to $8 \times$ ULN for > 2 weeks
 - AST or ALT $> 8 \times$ ULN
 - Total bilirubin $> 5 \times$ ULN
 - Concurrent AST or ALT $> 3 \times$ ULN and total bilirubin $> 2 \times$ ULN
- Grade 3 or 4 infusion reaction of any duration
- Any Grade 4 treatment -related AE or laboratory abnormality, except for the following events, which do not require discontinuation:
 - Grade 4 neutropenia ≤ 7 days.

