| Diarrhea or colitis, Grade 3 | 
 ● Withhold atezolizumab and tiragolumab for up to 12 weeks after event onset.^a ● Refer patient to GI specialist for evaluation and confirmatory biopsy. ● Initiate treatment with corticosteroids equivalent to 1–2 mg/kg/day IV methylprednisolone and convert to 1–2 mg/kg/day oral prednisone or equivalent upon improvement. If event does not improve within 48 hours after initiating corticosteroids, consider adding an immunosuppressive agent. ● If event resolves to Grade 1 or better, resume atezolizumab and tiragolumab.^b ● If event does not resolve to Grade 1 or better while withholding atezolizumab and tiragolumab, permanently discontinue atezolizumab and tiragolumab and contact Medical Monitor.^c |
| Diarrhea or colitis, Grade 4 | 
 ● Permanently discontinue atezolizumab and tiragolumab and contact Medical Monitor.^c ● Refer patient to GI specialist for evaluation and confirmatory biopsy. ● Initiate treatment with corticosteroids equivalent to 1–2 mg/kg/day IV methylprednisolone and convert to 1–2 mg/kg/day oral prednisone or equivalent upon improvement. ● If event does not improve within 48 hours after initiating corticosteroids, consider adding an immunosuppressive agent. ● If event resolves to Grade 1 or better, taper corticosteroids over \geq 1 month. |

| Event | Management |
|-------|------------|
|-------|------------|

GI = gastrointestinal.

- ^a Atezolizumab and tiragolumab may be withheld for a longer period of time (i.e., > 12 weeks after event onset) to allow for corticosteroids (if initiated) to be reduced to the equivalent of ≤ 10 mg/day oral prednisone. The acceptable length of the extended period of time must be based on the investigator's benefit-risk assessment and in alignment with the protocol requirements for the duration of treatment and documented by the investigator.
- ^b If corticosteroids have been initiated, they must be tapered over ≥ 1 month to the equivalent of ≤ 10 mg/day oral prednisone before atezolizumab and tiragolumab can be resumed.
- ^c Resumption of atezolizumab and tiragolumab may be considered in patients who are deriving benefit and have fully recovered from the immune-mediated event. Patients can be re-challenged with atezolizumab and tiragolumab only after approval has been documented by the investigator.

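### Section 6.2.1 stops treatment for Grade 3-4 treatment-related adrenal insufficiency and Grade 3 treatment-related colitis, but the Section 6.3 tables resume both drugs after recovery, and no clause says which governs

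*Combined protocol and SAP*

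**What the plan says.** **Adrenal insufficiency.** Section 6.2.1 lists when study treatment must stop for drug-related adverse events. For adrenal insufficiency of Grade 3 or higher, "treatment needs to be discontinued regardless of control with hormone replacement". Its one qualification is a note: "Hospitalization for diagnostic workup of adrenal insufficiency without severe symptoms should not require discontinuation". The Section 6.3.4 row covers Grades 2 to 4 together. It withholds both drugs for up to 12 weeks, refers the patient to an endocrinologist, and calls for imaging and corticosteroids. It then says "If event resolves to Grade 1 or better and patient is stable on replacement therapy, resume atezolizumab and tiragolumab". Footnote b to that line adds a condition ("If corticosteroids have been initiated, they must be tapered over" at least one month, down to 10 mg/day of prednisone or less). The row stops both drugs permanently only if the event does not settle or the patient is not stable on replacement.

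**Diarrhea or colitis.** Section 6.2.1: "Grade 3 treatment-related uveitis, pneumonitis, bronchospasm, diarrhea, colitis, neurologic toxicity, hypersensitivity reaction, or infusion reaction of any duration requires discontinuation". The Grade 3 row in Section 6.3.3 withholds for up to 12 weeks and then says "If event resolves to Grade 1 or better, resume atezolizumab and tiragolumab".

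**Thyroid.** The Grade 3-4 hypothyroidism and hyperthyroidism rows in Section 6.3.4 each have a line on resuming once symptoms are controlled and thyroid function is improving. The next line stops atezolizumab permanently. Neither row says what separates the two outcomes.

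**The concern.** Stability on hormone replacement is what Section 6.2.1 says does not matter after a Grade 3-4 adrenal event, and it is what Section 6.3.4 uses to allow re-dosing. The tables are where a site will look when managing a named event, so a patient who must stop under one section could be re-treated under the other. In a multicenter trial, two sites could handle the same event differently, each in line with a part of the protocol.

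These are anticipated toxicities: Section 7.1.3.1 lists both adrenal insufficiency and colitis as adverse events of special interest. Section 2.0 also counts discontinuations due to treatment-related adverse events in the safety endpoint, so that count would partly reflect which section each site followed. (The safety definition in Section 14.3 leaves discontinuations out, which is a separate matter.)

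**Working it through.** No arithmetic applies. The check sets the rules side by side by event and grade.

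| Event | Section 6.2.1 | Section 6.3 table | Result |
|---|---|---|---|
| Adrenal insufficiency, Grade 2 | Adrenal rule starts at Grade 3 | Hold, then resume | No conflict |
| Adrenal insufficiency, Grade 3 or 4 | Stop, even if controlled on replacement | Hold, then resume at Grade 1 or better, stable on replacement, steroids tapered | Conflict |
| Same, but only a diagnostic hospital stay without severe symptoms | Stopping not required | Hold, then resume | Compatible |
| Diarrhea or colitis, Grade 3, treatment-related | Stop, whatever the duration | Hold, then resume at Grade 1 or better | Conflict |
| Diarrhea, Grade 3, another cause established | Rule does not apply | Hold, then resume | Compatible |
| Thyroid, Grade 3 or 4 | May continue if controlled; at Grade 4, with Medical Monitor approval | Resume and permanent stop both listed | Table incomplete |

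**Is the 6.2.1 adrenal rule deliberate?** It appears so. Section 6.2.1 also takes adrenal insufficiency out of its Grade 3 endocrinopathy exemption and out of its Grade 4 exemption. The same sentence sets a Grade 4 threshold for hypophysitis, and the 6.3.4 table gives Grade 4 hypophysitis its own permanent-discontinuation row. The adrenal row was not split in that way.

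**Could discontinuation in 6.2.1 mean a temporary hold?** Not on the wording. Section 6.2 has separate terms for suspending, holding and interrupting treatment, and 6.2.1 is headed as discontinuation criteria.

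**Does any other clause reconcile the sections?** Three candidates, none sufficient:
- Footnote c to the adrenal row says "Resumption of atezolizumab and tiragolumab may be considered in patients who are deriving benefit and have fully recovered from the immune-mediated event". It is attached to the line on permanent discontinuation. The resume line carries footnote b, so resumption is the row's ordinary path and not a case-by-case re-challenge.
- Section 6.0 says "Other holds and modifications beyond what is described below may be made at the discretion of the PI". That covers steps additional to those described. It does not rank two rules that are both described.
- The diagnostic-hospitalization note in 6.2.1 removes one kind of event from the conflict and leaves the rest.

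**Do the design figures move?** No. The Simon rules in Section 14.5 (3 or more of 18; 8 or more of 43) rest on ctDNA results at C3D1. The boundary in Section 14.7.1 counts patients with a treatment-related event of Grade 3 or greater. A patient with such an adrenal event is already counted before the choice between stopping and resuming arises.

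**The case against.** The best defence is that the 6.3 tables are management guidelines read under the firmer criteria of 6.2.1, that few patients will be affected, and that the PI can settle individual cases. The small number is fair, and the documents give nothing to set against it. The rest does not answer the point: the tables instruct sites to resume, and no sentence subordinates them to 6.2.1.

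The other side is right on several limits. The colitis conflict exists only for treatment-related events, and Section 6.3.3 itself asks for other causes to be evaluated. Work-up hospitalizations without severe symptoms are not in conflict. Pancreatitis is uncertain: Section 7.1.3.1 lists it under endocrinopathies, which 6.2.1 names among the exceptions to its 7-day rule, although control by hormone replacement would rarely fit it.

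Two stronger readings are tempting and are not supported.

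- A reader might infer that the conflict alters the 18 Stage 1 patients, because Section 5.3 replaces those who discontinue before C3D1 and a 12-week hold is longer than two 28-day cycles. That comparison shows nothing. The sample is taken before dosing on C3D1, so a hold would ordinarily delay C3D1 itself. A patient whose event never settles is discontinued under either text. Only patients who would resume could be treated differently, and no rate for them is available.
- A reader might infer that one section is always the safer one, so that a single precedence sentence would do. For Grade 3 AST or ALT elevation, 6.2.1 stops treatment in most cases, adds fixed stopping limits, and permits continuation after discussion with the Medical Monitor. The 6.3.2 table says permanent discontinuation, with a re-challenge footnote. Neither is clearly the laxer, so a blanket ranking either way lacks support.

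**Conclusion.** The inconsistency is real and should be fixed. It is direct for Grade 3-4 treatment-related adrenal insufficiency, outside the diagnostic-hospitalization exception, and for Grade 3 treatment-related diarrhea or colitis. The two Grade 3-4 thyroid rows are incomplete as written. Grade 3 myositis and pancreatitis may also conflict with the 6.2.1 rule on Grade 3 or higher non-skin related events that last more than 7 days or recur. That is a matter for clinical checking and is not asserted here.

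The consequence is for patient safety, uniform conduct and the discontinuation count in Section 2.0. It does not reach the sample size, the Simon thresholds or the toxicity boundary. No incidence is given, so neither a number of patients nor a shift in any proportion can be stated. The conclusion assumes that 6.2.1 and the 6.3 tables address the same drug-related events, as their headings indicate.

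**What to change.** 1. **Adrenal row.** Split it. Grade 2 keeps the present text. For Grade 3-4, keep the endocrinologist referral, imaging and corticosteroid instructions. Replace the withhold and resume lines with permanent discontinuation of both drugs, whatever the control on hormone replacement, and contact with the PI. Leave footnote c off that line, since it would reopen re-dosing by another route. State that a patient graded 3 only because of a diagnostic hospital stay without severe symptoms follows the Grade 2 hold and resume text.
2. **Grade 3 diarrhea or colitis row.** Require permanent discontinuation for treatment-related events and keep the supportive-care text. Keep hold and resume only where another cause is established.
3. **Grade 3-4 thyroid rows.** State the condition that separates resuming from stopping, in agreement with the Grade 3 and Grade 4 endocrinopathy exemptions in 6.2.1.
4. **Remaining Grade 3 rows.** Have the clinical team check them, myositis and pancreatitis among them, against the 7-day rule.

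If re-dosing is intended in any of these cases, amend 6.2.1 instead. The cost is an IRB-approved wording amendment and a short clinical review, with no change to sample size, visits or analysis.

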 - Grade 4 lymphopenia or leukopenia ≤ 14 days in duration.
 - Isolated Grade 4 amylase or lipase abnormalities that are not associated with symptoms or clinical manifestations of pancreatitis and decrease to Grade < 4 or return to baseline within 7 days.
 - Isolated Grade 4 electrolyte imbalances/abnormalities that are not associated with clinical sequelae and are corrected with supplementation/appropriate management within 72 hours of their onset.
 - Grade 4 treatment -related endocrinopathy AEs (except adrenal insufficiency or hypophysitis), such as hyper- or hypothyroidism, or glucose intolerance, which resolve or are adequately controlled with physiologic hormone replacement (corticosteroids at ≤ 10 mg of prednisone or equivalent per day, thyroid hormones) or glucose-controlling agents,

respectively, may not require discontinuation after discussion with and approval from the Medical Monitor.

- Any AE, laboratory abnormality, or intercurrent illness that, in the judgment of the Investigator, presents a substantial clinical risk to the patient with continued treatment.
- Disease recurrence (local, regional, or distant), including new primary melanoma (except MMIS Stage 0) Note: Non-melanoma skin cancer does not require treatment discontinuation. In the absence of intolerable toxicity, patients with diagnosed MMIS Stage 0 melanoma will be eligible to continue study treatment using the same dose and schedule for their original melanoma of up to approximately 1 year of study treatment starting from first dose, at the discretion of the Investigator.

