6.3.6 Eye Disorders or Events

An ophthalmologist should evaluate visual complaints (e.g., uveitis, retinal events). Management guidelines for ocular events are provided in the table below.

Management Guidelines for Eye Disorders or Events

| Event | Management |
|------------------------|--|
| Eye disorders, Grade 1 | 
 ● Continue atezolizumab and tiragolumab. ● Patient referral to ophthalmologist is strongly recommended. |

| Event | Management |
|-----------------------------|---|
| | 
 ● Initiate treatment with topical corticosteroid eye drops and topical immunosuppressive therapy. ● If symptoms persist, treat as a Grade 2 event. |
| Eye disorders, Grade 2 | 
 ● Withhold atezolizumab and tiragolumab for up to 12 weeks after event onset.^a ● Patient referral to ophthalmologist is strongly recommended. ● Initiate treatment with topical corticosteroid eye drops and topical immunosuppressive therapy. ● If event resolves to Grade 1 or better, resume atezolizumab and tiragolumab.^b ● If event does not resolve to Grade 1 or better while withholding atezolizumab and tiragolumab, permanently discontinue atezolizumab and tiragolumab and contact PI.^c |
| Eye disorders, Grade 3 or 4 | 
 ● Permanently discontinue atezolizumab and tiragolumab and contact PI.^c ● Refer patient to ophthalmologist. ● Initiate treatment with corticosteroids equivalent to 1–2 mg/kg/day oral prednisone. ● If event resolves to Grade 1 or better, taper corticosteroids over ≥ 1 month. |

^a Atezolizumab and tiragolumab may be withheld for a longer period of time (i.e., ≥ 12 weeks after event onset) to allow for corticosteroids (if initiated) to be reduced to the equivalent of ≤ 10 mg/day oral prednisone. The acceptable length of the extended period of time must be based on the investigator's benefit-risk assessment and in alignment with the protocol requirements for the duration of treatment and documented by the investigator.

^b If corticosteroids have been initiated, they must be tapered over ≥ 1 month to the equivalent of ≤ 10 mg/day oral prednisone before atezolizumab and tiragolumab can be resumed.

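### Section 6.2.1 requires a stop for treatment-related Grade 3 diarrhea/colitis and for Grade 3 or higher adrenal insufficiency, the 6.3.3 and 6.3.4 tables order both drugs resumed on recovery, and nothing ranks the sections

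*Combined protocol and SAP*

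**What the plan says.** Section 6.2.1 lists the adverse events for which study treatment must end. For Grade 3 or higher adrenal insufficiency it says that "treatment needs to be discontinued regardless of control with hormone replacement". Its one qualification is a note that being hospitalized for diagnostic workup, without severe symptoms, should not force a stop. The allowance for controlled Grade 4 endocrine events covers "endocrinopathy AEs (except adrenal insufficiency or hypophysitis"), so adrenal insufficiency gets no relief there. For a further group of events the rule is: "Grade 3 treatment-related uveitis, pneumonitis, bronchospasm, diarrhea, colitis, neurologic toxicity, hypersensitivity reaction, or infusion reaction of any duration requires discontinuation".

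Section 6.3 then gives event-by-event management tables. In Section 6.3.3, the Grade 3 diarrhea/colitis row calls for a hold of up to 12 weeks, specialist evaluation and corticosteroids, followed by: "If event resolves to Grade 1 or better, resume atezolizumab and tiragolumab". In Section 6.3.4, a single row covers adrenal insufficiency of Grades 2 to 4. It also begins with a hold of up to 12 weeks, and it ends: "If event resolves to Grade 1 or better and patient is stable on replacement therapy, resume atezolizumab and tiragolumab".

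**The concern.** For a patient who recovers from either event, a site cannot follow both sections. The adrenal conflict is the plainest. Control on replacement therapy is what Section 6.2.1 declares irrelevant, and it is what Section 6.3.4 makes the condition for restarting.

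At stake is whether a patient with completely resected disease is re-exposed to one or two checkpoint inhibitors after a severe immune-mediated event. In a multicenter trial that should not depend on which page the treating physician opens.

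**Working it through.** No arithmetic applies, because the plan states no figure on this point. The check is a comparison of rows, followed by a search for text that would settle the differences.

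**Unconditional comparison**

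| Event | Section 6.2.1 | Section 6.3 table | Result |
|---|---|---|---|
| Diarrhea/colitis, Grade 3, treatment-related | Stop, any duration | Hold, then resume (6.3.3) | Conflict |
| Diarrhea/colitis, Grade 4, treatment-related | Stop | Stop permanently (6.3.3) | Agree |
| Adrenal insufficiency, Grade 2 | No stop required | Hold, then resume (6.3.4) | Agree |
| Adrenal insufficiency, Grades 3 and 4 | Stop, even if controlled | Hold, then resume if stable on replacement (6.3.4) | Conflict |

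**Conditional conflicts (a non-exhaustive list)**

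- *Grade 3 myositis lasting more than 7 days.* Section 6.2.1 stops any Grade 3 or higher "non-skin, treatment-related AE lasting > 7 days or recurs", and myositis is not among the exceptions. The Grade 3 row of Section 6.3.15 allows a hold of up to 12 weeks and then resumption.
- *Grade 2 uveitis.* Section 6.2.1 stops treatment if the event fails topical therapy and "does not improve to Grade 1 severity within 8 weeks", or if it needs systemic treatment. The second trigger has no time limit. The Grade 2 row of Section 6.3.6 says "Withhold atezolizumab and tiragolumab for up to 12 weeks after event onset" and then permits resumption. On the first trigger, the table's hold outlasts the 6.2.1 limit by 12 − 8 = 4 weeks.
- *Grade 4 amylase or lipase elevation.* Section 6.2.1 spares an isolated, symptom-free elevation only if it drops below Grade 4 or returns to baseline within 7 days. The Grade 3 or 4 row of Section 6.3.10 allows a hold of up to 12 weeks and then resumption.

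**Search for text that reconciles or ranks the sections**

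- Section 6.0 gives the PI discretion over holds and modifications other than those described. It does not choose between two that are described.
- Section 6.2 governs how long a hold may last and who may extend it.
- Section 5.6 adds investigator judgment as a ground for stopping. It does not rank 6.2.1 against 6.3.
- The re-challenge footnote (c) in 6.3.3 and 6.3.4 attaches to the permanent-discontinuation bullets. The disputed resumption bullets carry footnote b, which concerns only the steroid taper.
- Discontinuation in 6.2.1 cannot be read as a temporary hold. The section is a list of discontinuation criteria, and holds are dealt with separately in 6.2.

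**What in the analysis could move**

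- *Discontinuations due to treatment-related AEs.* These are part of the safety endpoint in Section 2.0 (the Section 14.3 definition omits them). They could differ according to the section a site follows.
- *Number of treatment-related Grade 3 or higher AEs (Section 14.3).* This could also differ, because a patient who resumes has more exposure and a longer observation window in which to have further events.
- *Stage 1 replacement (Section 5.3).* This applies to patients who discontinue before C3D1, so it could differ for an event that early.
- *Stopping boundaries (Section 14.7.1).* These count patients with toxicity. A patient already counted for the Grade 3 event is not counted again, so the boundary tally for that patient is the same either way.

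**The case against.** The strongest reply is that the wording already implies a ranking. Section 6.2.1 speaks of requirements, while Section 6.3 is headed as guidelines, so a site that resumes has overridden a requirement. Safeguards also exist. Colitis and adrenal insufficiency are adverse events of special interest reportable within 24 hours (Section 7.1.3.1). Resumption needs recovery to Grade 1 and, where steroids were given, a taper of at least a month. Section 6.2.1 also stops treatment for any event the investigator judges a substantial risk.

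The wording does lean toward 6.2.1, and the safeguards reduce the risk. Neither removes the contradiction. The tables do not merely permit resumption, they instruct it, and the event-specific table is what a clinician managing the event is likely to consult. Where 6.2.1 intends discretion it says so, as for Grade 3 AST/ALT elevation. It gives none for the two core events beyond the adrenal workup note.

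Three further objections stand and limit the point:

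- A reader might infer that every Grade 3 diarrhea/colitis case must stop. Section 6.2.1 covers only treatment-related cases, whereas the 6.3.3 row is not so limited and calls for evaluation and biopsy.
- A reader might take the conflicting rows above as a full count. They are not. Grade 3 hypophysitis and Grade 3 pancreatitis, for example, are arguable under the 7-day rule.
- Re-challenge footnotes also sit under permanent-discontinuation rows, such as Grade 3 or 4 infusion reactions (6.3.8), eye disorders (6.3.6) and neuropathy (6.3.12), and Grade 4 hypophysitis (6.3.4). They are a milder matter, because a site that stops complies with both sections.

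**Conclusion.** The contradiction is real and should be corrected. Two table rows order resumption where Section 6.2.1 requires a stop, and at least three more do so under stated conditions. The conclusion assumes that the diarrhea/colitis event is treatment-related, that the adrenal event is Grade 3 or 4, and that the patient recovers enough to meet the table's condition for restarting.

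The consequence is for patient safety and uniform conduct across sites. The documents give no rate for these events at these grades, so neither a patient count nor a statistical effect is estimated. That few patients are likely to be affected is a judgment.

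A reader might infer that the toxicity stopping rule is compromised. The documents do not support that, since its boundaries count patients and the event counts whether the patient stops or resumes. A reader might equally infer that no safety summary can change. That goes too far the other way, because the number of Grade 3 or higher AEs and the discontinuations could both move.

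**What to change.** 1. Add one sentence to Section 6.2.1: its mandatory stops prevail over the Section 6.3 tables and footnotes, except where 6.2.1 itself names an exception. This also settles the conditional rows and the re-challenge footnotes without editing each one.
2. In Section 6.3.3, change the Grade 3 row to permanent discontinuation for treatment-related diarrhea or colitis only. Keep withholding and evaluation until attribution is settled.
3. In Section 6.3.4, split the adrenal insufficiency row into Grade 2 (withhold, then resume) and Grades 3 to 4 (discontinue). Carry over the 6.2.1 note on hospitalization for diagnostic workup without severe symptoms.

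If the sponsor prefers to allow re-challenge for a given event, that should be written as a named exception in 6.2.1, stating who approves it. Which clinical rule to keep is the sponsor's choice; the documents only need to state one.

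The cost is amendment wording, with no new visits or data. The downside is a small loss of investigator discretion to re-treat recovered patients.
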